6.3. Study Restrictions

6.3.1. Contraception Restrictions

Male subjects with a female sexual partner of child-bearing potential must wear a condom (from first dosing until 3 months after final dosing) in addition to their female partner using a highly effective method of contraception, from first dosing until 3 months following final dosing. Contraceptive methods that can achieve a failure rate of less than 1% per year when

used consistently and correctly are considered as highly effective birth control methods. Such methods include:

- Combined (estrogen and progestogen containing) hormonal contraception associated with inhibition of ovulation:
 - Oral
 - Intravaginal
 - Transdermal
- Progestogen-only hormonal contraception associated with inhibition of ovulation
 - Oral
 - Injectable
 - Implantable
- Intrauterine device or intrauterine hormone-releasing system
- Bilateral tubal occlusion
- Surgical sterilisation

If the male subject is vasectomised then this will be accepted as a second form of highly effective contraception, in addition to the subject also wearing a condom. Sexual abstinence is considered a highly effective method only if defined as refraining from heterosexual intercourse during the entire period of risk associated with study treatment and must be part of the preferred and usual lifestyle of the subject.

6.3.2. Lifestyle Restrictions

Subjects should abstain from strenuous exercise for 48 hours prior to each visit for blood collection for clinical laboratory tests, and while in the CRU. Subjects should not start any new exercise regimes during their participation in the study.

6.3.3. Meals and Dietary Restrictions

The subjects are required to adhere to the following restrictions:

- Subjects should refrain from consumption of any food or drinks containing cranberry, pomegranate, starfruit, grapefruit, pomelos, exotic citrus fruits or Seville oranges (including marmalade and juices made from these fruits) within 14 days prior to first dosing until the end of the study.
- Subjects should abstain from alcohol for 48 hours prior to Screening and no alcohol should be consumed from 48 hours prior to Day -1 until the end of the study.
- Subjects should abstain from tobacco and nicotine-containing products for 3 months prior to Screening, throughout the study until completion of the study.
- Subjects should abstain from (methyl) xanthine- and caffeine-containing products for 48 hours prior to each clinic visit until the end of the study.

- Subjects will be fasted overnight before dosing. Water will be allowed ad libitum and breakfast can be eaten between 1 to 2 hours after dosing. Standard meals and drinks will be provided while resident in the CRU. In addition, subjects should fast at least 4 hours prior to any visit where clinical laboratory evaluations will be carried out.
- Subjects should refrain from consuming poppy seeds 48 hours prior to Screening, Day -1, Day 14, Day 21 and Day 28 to avoid a positive result on the drugs of abuse screen.

6.4. Subject Withdrawal Criteria

For all subjects withdrawn from the study, discontinuation procedures as described in [Appendix 1](#) should be conducted prior to discharge in the study. Subjects will be replaced if there are insufficient evaluable subjects in each dose cohort. A minimum of 4 ivermectin and 1 placebo subjects in each cohort are required for dose escalation and a minimum of 5 ivermectin and 1 placebo subjects are required for completion of a dose cohort.

Reserve subjects will be screened and admitted to the CRU on Day -1. They will undergo the Day -1 and pre-dose assessments but will not be dosed on Day 1, unless replacing another subject who fails inclusion/exclusion criteria.

Reasons for withdrawal or discontinuation at any time during the study may include any of the following reasons:

- Adverse event: Clinical or para-clinical events occurred that, in the medical judgement of the Investigator for the best interest of the subjects, are grounds for discontinuation. This includes serious and non-serious AEs regardless of relation to the study medication.
- Withdrawal of consent: The subject desired to withdraw from further participation in the study in the absence of an Investigator determined medical need to withdraw. If the subject gave a reason for withdrawing it should be recorded in the eCRF.
- Investigator decision.
- Compliance: any subject who fails to take their daily dose for 2 consecutive days, misses 3 doses in a week (7 days), or misses greater than 1 dose of study drug per week (>4 in total during 4-week study).
- Lost to follow-up: The subject stopped coming for visits and study personnel were unable to contact the subject.
- Other: The subject was discontinued for a reason other than those listed above, such as termination of the study by the Sponsor. The reason(s) should be recorded in the eCRF.

6.5. Follow-up Procedures

The Investigator will make diligent attempts to contact subjects who fail to return for a scheduled visit or were otherwise unable to attend the follow-up visit. All discontinuations and the reason for early discontinuation will be documented by the Investigator, and if appropriate on the AE form.

7. SAFETY ASSESSMENTS

Baseline safety data assessments for all parts of the study will be collected pre-dose at the nearest timepoint to dosing as shown in [Appendix 1](#). The subjects will attend a Follow-up visit 14 days after the final dose for safety follow-up procedures

7.1. Clinical Laboratory Evaluations

Clinical laboratory evaluations will be performed including clinical chemistry, haematology, coagulation and urinalysis as indicated in the table below ([Table 5](#)). Serology, drugs of abuse, cotinine and alcohol screen will be performed as indicated in the table below ([Table 5](#)).

All blood and urine analyses will be conducted at the sampling times. The clinical laboratory evaluation results will be collected at Day -1, in time for results to be reviewed prior to dose administration. For abnormal values, additional testing may be performed, or clinical laboratory evaluations may be added to evaluate the abnormal values. Clinically significant values should be followed until resolution or until they reach a stable state.

Table 5: Clinical Laboratory Evaluations

Blood Chemistry BUN Creatinine Glucose Sodium Potassium Phosphate Chloride Calcium AST ALT GGT Alkaline phosphatase Total bilirubin Uric acid Albumin Total protein Lactate dehydrogenase	Urinalysis (dipstick) Glucose Bilirubin Ketone Specific Gravity Blood pH Protein Urobilinogen Nitrite Leukocyte Esterase Microscopic analysis if dipstick is abnormal
Haematology Haemoglobin Haematocrit RBC count RBC indices (MCV, MCH, MCHC) Platelet count White blood cell count with differential	Drugs of abuse Amphetamines Barbiturates Benzodiazepines Cocaine Cannabinoids Opiates
Coagulation Prothrombin time International normalization ratio Activated partial thromboplastin time	Serology Anti-HIV I/II SARS-CoV-2 (performed only if lateral flow immunoassay testing is positive)
Other Screens Alcohol (breath) Cotinine (urine) SARS-CoV-2 RT-PCR test	Anti-HCV HBsAg

Abbreviations: ALT – alanine aminotransferase; Anti-HIV I/II – Anti-human immunodeficiency virus I and II; Anti-HCV – anti-hepatitis C antibody; AST: aspartate aminotransferase; BUN – blood urea nitrogen; GGT – gamma-glutamyl transferase; HBsAG – hepatitis B surface antigen; MCV – mean corpuscular volume; MCH – mean corpuscular haemoglobin; MCHC – mean corpuscular haemoglobin concentration; RT-PCR – reverse transcription polymerase chain reaction.

7.2. 12-lead Electrocardiogram

A 12-lead ECG will be collected at the timepoints indicated in the Schedule of Assessments. The 12-lead ECG will be collected in triplicate, approximately 1 minute apart, at Screening, Day -1 and within 2 hours pre-dose on Day 1. Single readings will be collected at all other timepoints. 12-lead ECGs should be obtained after the subject has rested in the supine position for at least 5 minutes. In the event of an abnormal finding, recordings should be performed in triplicate. The ECG machine used should automatically calculate the heart rate and PR, RR, QRS, QT and QTcF intervals.

For timepoints with multiple assessments:

- collect the ECG first,
- then vital signs,
- then the PK blood draw. The PK sample should be collected at the scheduled time post-dose.

7.3. Vital Signs and Oral Temperature

Supine and standing vital signs (2 minutes apart), including heart rate, blood pressure and oral temperature will be collected at the timepoints in the Schedule of Assessments. Pre-dose vital signs should be collected within 30 minutes pre-dose.

For timepoints with multiple assessments:

- collect the ECG first,
- then vital signs,
- then the PK blood draw. The PK sample should be collected at the scheduled time post-dose.

7.4. Physical Examinations

A full physical examination, including height, BMI, and body weight, and assessments of the head, eyes, ears, nose, throat, skin, thyroid, neurological, lungs, cardiovascular system, abdomen (liver and spleen), lymph nodes and extremities will be conducted at the times indicated in the Schedule of Assessments. A symptom-guided physical examination will also be conducted at the times indicated in the Schedule of Assessments.

7.5. Neurological Examinations

A comprehensive neurological examination will be conducted at the times specified in the Schedule of Assessments. The comprehensive neurological examination will include assessment of mental status and cognitive function, cranial nerve examination, motor function, sensation and proprioception (light touch, vibration), deep tendon reflexes of all 4 limbs, balance, co-ordination, gait and visual assessments. Visual assessments will include

visual inspection of the eyes, pupil response, eye movements, fundoscopy, visual acuity (Snellen chart) and visual fields.

7.6. Adverse Event Reporting

Adverse event monitoring will be conducted at the times specified in the Schedule of Assessments. Adverse events will be elicited through non-leading questions and spontaneous reporting by subjects. The Investigator is responsible for evaluating AEs and for the appropriate medical care of subjects during the study.

7.6.1. Definition and Criteria

7.6.1.1. Adverse Event

An AE is any untoward medical occurrence in a study subject which either emerges, or worsens from Screening, during the clinical study, regardless of its potential relationship to the medicinal product. An AE, therefore, can be any unfavourable or unintended sign, including a clinically significant abnormal laboratory finding, symptom, or disease temporally, whether or not it is considered to be study medication related.

Examples of an AE include:

- Exacerbation of a pre-existing condition including either an increase in frequency and/or intensity of the condition.
- New conditions detected or diagnosed.
- Signs or symptoms of a drug interaction.
- Signs or symptoms of a suspected overdose of either IMP or a concurrent medication (overdose per se should not be reported as an AE/SAE)
- A new laboratory abnormality occurring after the start of the study (i.e., after Screening) that results in subject withdrawal from the study or medical treatment or further follow-up.
 - Note: abnormal laboratory or other values obtained during Screening that preclude a subject from entering the study are not considered AEs but will be recorded.

Adverse events may include pre- or post-treatment events that occur as a result of Protocol-mandated procedures (i.e., invasive procedures, modification of subject's previous therapeutic regimen).

A medical intervention to address an AE is an "action taken" and not an AE itself.

7.6.1.2. Serious Adverse Event

An SAE is any untoward medical occurrence that, at any dose:

- Results in death,
- Is life-threatening,
 - Note: The term 'life-threatening' in the definition of 'serious' refers to an event in which the subject was at risk of death at the time of the event. It does not refer

to an event, which hypothetically might have caused death, if it were more severe.

- Requires hospitalisation or prolongation of existing hospitalisation,
 - Note: In general, hospitalisation signifies that the subject has been detained (usually involving at least an overnight stay) at the hospital or emergency ward for observation and/or treatment that would not have been appropriate in the physician's office or out setting. Complications that occur during hospitalisation are AEs. If complication prolongs hospitalisation or fulfils any other serious criteria, the event is serious. When in doubt whether 'hospitalisation' occurred or was necessary, the AE should be considered serious.
- Results in persistent or significant disability or incapacity,
 - Note: The term 'disability' means a substantial disruption of a person's ability to conduct normal life functions. This definition is not intended to include experiences of relatively minor medical significance such as uncomplicated headache, nausea, vomiting, diarrhoea, influenza and accidental trauma (e.g., sprained ankle) which may interfere or prevent everyday life functions but do not constitute a substantial disruption.
- Is a congenital abnormality or birth defect,
- Is an important medical event.
 - Note: Medical or scientific judgement should be exercised in deciding whether reporting is appropriate in other situations, such as important medical events that may not be immediately life threatening, or result in death or hospitalisation, but may jeopardise the subject or may require medical or surgical intervention to prevent one of the other outcomes listed in the above definition. These should also be considered serious. Examples of such events are invasive or malignant cancers, intensive treatment in an emergency room or at home for allergic bronchospasm, blood dyscrasias or convulsions that do not result in hospitalisation, or development of drug dependency or drug abuse.
 - Note: The terms "serious" and "severe" ARE NOT synonymous. The term "severe" is often used to describe the intensity (severity) of a specific event (as in mild, moderate or severe myocardial infarction); the event itself, however, may be of relatively minor medical significance (such as severe headache). This is NOT the same as "serious", which is based on subject/event outcome or action criteria described above and are usually associated with events that pose a threat to a subject's life or functioning. A severe AE does not necessarily need to be considered serious. For example, persistent nausea of several hours duration may be considered severe nausea but not an SAE. On the other hand, a stroke resulting in only a minor degree of disability may be considered mild but would be defined as an SAE based on the above criteria. Seriousness (not severity) serves as a guide for defining regulatory reporting obligations.

7.6.1.3. Clinical Laboratory Abnormalities and Other Abnormal Assessments as Adverse Events and Serious Adverse Events

Abnormal laboratory findings (e.g., clinical chemistry and haematology) or other abnormal assessments (e.g., ECGs, vital signs) that are judged by the Investigator as clinically significant will be recorded as AEs or SAEs if they meet the definition of an AE or SAE. Clinically significant abnormal laboratory findings or other abnormal assessments that are detected during the study or are present at baseline and significantly worsen following the start of the study will be reported as AEs or SAEs. The Investigator will exercise his or her medical and scientific judgment in deciding whether an abnormal laboratory finding, or other abnormal assessment is clinically significant. Liver chemistry thresholds have been designed to assure subject safety. When subjects meet the hepatic transaminase threshold criteria (AST or ALT ≥ 3 x ULN), the subject should undergo close observation, including monitoring for symptoms (clinical symptoms of hepatitis, or hypersensitivity, fatigue, decreased appetite, nausea, vomiting, abdominal pain, jaundice, fever, or rash) and hepatic function (AST, ALT, ALP), and fractionated bilirubin at least every 48 hours, until symptoms and/or hepatic function abnormalities resolve, stabilise, or return to baseline values. This event should be reported to MedinCell within 24 hours of learning of its occurrence. [Appendix 4](#) represents the decision tree for whether or not study medication will be discontinued. A specialist or hepatology consultation should be considered in cases of protocol-mandated study medication discontinuation.

In addition, every attempt should be made to obtain the following for any subject who meets the hepatic transaminase threshold criteria:

- Viral hepatitis including: hepatitis A immunoglobulin (IgM) antibody, hepatitis B surface antigen and hepatitis B core antibody (IgM), HCV RNA, cytomegalovirus IgM antibody, Epstein-Barr viral capsid antigen IgM antibody (or if unavailable, obtain heterophil antibody or monospot testing), and hepatitis E antibody (if subject resides outside UK or has travelled outside UK in past 3 months).
- Serum creatine phosphokinase and lactate dehydrogenase. Record the appearance or worsening of clinical symptoms of hepatitis, or hypersensitivity, fatigue, decreased appetite, nausea, vomiting, abdominal pain, jaundice, fever, or rash as relevant on the AE report form.
- Record use of concomitant medications, including paracetamol, herbal remedies, other OTC medications, putative hepatotoxins, or alcohol on the concomitant medications report form.
- The following are required for subjects with AST or ALT ≥ 3 x ULN and bilirubin ≥ 2 x ULN, but are optional for other abnormal liver chemistries:
 - Anti-nuclear antibody, anti-smooth muscle antibody, and type 1 anti-liver kidney microsomal antibodies.
 - Liver imaging (ultrasound, magnetic resonance, or computerised tomography) to evaluate liver disease.

7.6.1.4. Pharmacokinetic Sampling Associated with Serious Adverse Events or Severe Adverse Events

Every possible attempt will be made to collect an unscheduled PK sample if a subject experiences an SAE or a severe AE. As the determination of an SAE or a severe AE is sometimes retrospective, unscheduled PK samples obtained when an event that is suspected to be serious or severe are also permitted.

7.6.2. Evaluating Adverse Events and Serious Adverse Events

All AEs will be assessed on 2 descriptive parameters: intensity (severity) and relationship to the study medication:

- Intensity refers to the severity of an event and references impact on a subject's functioning.
- Relationship refers to the likelihood that the event being assessed was caused by the study medication.

The intensity of each AE (including SAEs) will be recorded in the eCRF and assigned to one of the following categories:

- **Mild:** An event that is easily tolerated by the subject, causing minimal discomfort and not interfering with everyday activities.
- **Moderate:** An event that is sufficiently discomforting to interfere with normal everyday activities.
- **Severe:** An event that prevents normal everyday activities.

For AEs and SAEs, the relationship to the study treatment is to be assessed according to the following definitions:

Not related: There is no reasonable association between the study treatment and the suspected event.

Unlikely related: It is doubtful that there is an association between the study treatment and the suspected event. The event could have been produced by the subject's clinical state or other modes of therapy administered to the subject.

Possibly related: The suspected AE may or may not follow a reasonable temporal sequence from study drug administration. The event could have been produced or mimicked by the subject's clinical state or by other modes of therapy concomitantly administered to the subject.

Probably related: The suspected AE follows a reasonable temporal sequence from study treatment administration, abates upon discontinuation of the treatment; and cannot be reasonably explained by the known characteristics of the subject's clinical state.

When assessing the relationship to the study medication, the following criteria will be considered:

- Known class effect
- Positive rechallenge

- Positive dechallenge (resolution upon stopping the suspect study medication, in absence of other interventional treatment]
- Biological plausibility
- Lack of alternative explanation – concomitant drug or disease

7.6.3. Reporting Procedures and Requirements

7.6.3.1. Adverse Events

Events meeting the criteria in [Section 7.6.1.1](#) occurring from the time of signed informed consent will be considered as AEs. All AEs between Screening to the Follow-up visit will be recorded in source and eCRF, whether or not considered study medication related. All AEs that are possibly or probably related to study medication will be followed until resolution or database lock, whichever occurs first. Also, the sign, symptom, or disease present before the baseline AE assessment are only considered AEs if they worsen after this point. Any AEs already documented at a previous assessment and designated as ongoing should be reviewed at subsequent visits as necessary. If these have resolved, this should be documented. Changes in intensity or frequency of AEs should be recorded as separate events (i.e., a new record started). The Investigator should report all AEs on the AE page(s) of the eCRF and source documents, regardless of seriousness, severity, and causality. Whenever possible, an AE will be reported using a diagnostic term, (e.g., “common cold” or “upper respiratory infection” rather than “runny nose, cough, mild fever”) and should be described with the attributes described in [Section 7.6.1.1](#).

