Subjects will be required to attend the CRU for a Screening visit within 28 days prior to first dosing to ensure they meet the inclusion/exclusion criteria and are in good health. Subjects will be admitted to the CRU 1 day prior to first dosing (Day -1) for collection of baseline safety assessments and will receive their first dose of ivermectin or placebo in the morning of Day 1, following an overnight fast. Subsequent daily doses of ivermectin or placebo will be administered in the morning in the CRU from Day 2 to Day 7, following an overnight fast. Subjects will reside in the CRU until at least 4 hours post-dose on Day 7 for the collection of safety assessments and PK blood samples but may reside for longer if deemed necessary by the Investigator. From Day 8 to Day 27, subjects will self-administer their daily dose of ivermectin or placebo at home following an overnight fast, with the exception of outpatient visits on Day 14 and Day 21 which will be administered in the CRU. Subjects will be readmitted to the CRU on Day 28 to receive their final dose of ivermectin or placebo and will be discharged on Day 29 following safety assessments and PK blood samples. Subjects will return to the CRU for outpatient visits on Days 32, 35 and 42 for safety assessments and PK blood samples.

A detailed plan of study assessments is provided in [Appendix 1](#).

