4.6.1 Adverse Events

Adverse events will be listed in the following categories:

 Treatment-emergent adverse events (TEAEs) are any AEs with a start date and time on or after dosing with ivermectin/placebo. All TEAEs will be listed and summarised as indicated below

The overall incidence of TEAEs (number and percentage of subjects) as well as the number of events will be summarised by treatment, cohort and overall, categories of degree of severity, serious adverse events (SAEs), causally related TEAEs and SAEs, TEAEs leading to discontinuation of treatment and AEs or SAEs leading to withdrawal.

TEAEs will be summarised at both the subject [number (%) of subjects] and event [number of events] level for the following:

- System Organ Class (SOC) and PT
- SOC and PT and maximum reported severity
- SOC and PT and causal relationship to study drug

These analyses will be repeated for SAEs and treatment related AE if deemed necessary, otherwise only the SAEs by SOC and PT will be performed.

For the incidence at the subject level by SOC and PT; if a subject experiences more than one event within the same SOC and PT, only one occurrence will be included in the incidence.

For the incidence at the subject level by SOC, PT and severity; if a subject experiences more than one event within the same SOC and PT, only the most severe occurrence will be included in the incidence.

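### Successive records of one adverse event are each counted as an event, and the TEAE definition has no worsening condition

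*Protocol*

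**What the plan says.** Three rules meet here.

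- **Recording.** Protocol 7.6.3.1: "Changes in intensity or frequency of AEs should be recorded as separate events (i.e., a new record started". The sentence covers changes in either direction.
- **Classification.** SAP 4.6.1: "Treatment-emergent adverse events (TEAEs) are any AEs with a start date and time on or after dosing with ivermectin/placebo". The start is the only test. Nothing refers to the state of the event before dosing.
- **Counting.** SAP 4.6.1: "TEAEs will be summarised at both the subject [number (%) of subjects] and event [number of events] level for the following", after which it names tabulations by SOC and PT, by maximum severity and by causal relationship. SAP 4.1 also asks for numbers of events in AE summaries. The SAP removes repeats within SOC and PT, and keeps the most severe occurrence, only when it counts subjects.

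The protocol does set a limit for pre-existing conditions. Section 7.6.3.1 says that "the sign, symptom, or disease present before the baseline AE assessment are only considered AEs if they worsen after this point". The available text does not define the baseline AE assessment, and the SAP does not carry the limit into its TEAE definition.

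**The concern.** The recording rule makes sense for data collection, because it preserves the course of each event. The difficulty is that the SAP counts the resulting records with nothing in between to put them back together.

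Two consequences follow. First, a post-dose event that changes intensity or frequency enters the event-level tables several times. Second, a continuation record opened after dosing may turn an AE that began before dosing into a TEAE, even when the change is an improvement. The second would go against the protocol's own principle that a pre-existing sign must worsen before it counts.

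AE reporting is part of the secondary endpoint, and the safety analysis is descriptive. The counts are themselves the result, and in groups of six and two a single misclassified subject is visible.

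**Working it through.** The documents give no figure on this point, so there is nothing to reproduce. The check applies the rules literally to four invented AE histories and compares the counts with those under a linked rule.

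**Inputs from the documents**
- A new record at each change of intensity or frequency (Protocol 7.6.3.1).
- TEAE decided by start alone; events and subjects both reported; repeats removed only at subject level (SAP 4.6.1).
- Events "occurring from the time of signed informed consent will be considered as AEs" (Protocol 7.6.3.1), with a "Screening visit within 28 days prior to first dosing" (Protocol 3), so an AE can be ongoing at first dose.
- 6 ivermectin and 2 placebo subjects in each of 3 cohorts (Protocol 3). Pooled: 3 × 6 = 18 and 3 × 2 = 6.

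**Assumptions**
- Each new record starts on the date of the change.
- An AE with onset between consent and first dose is recorded as an AE.
- Comparison rule: the records of one AE are joined, and the joined episode is treatment-emergent if it began at or after first dose, or if its highest post-dose grade exceeds its highest pre-dose grade.

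**Step 1: records per episode.** Records = k + 1 for k changes. Mild, moderate, mild has k = 2, so 2 + 1 = 3.

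**Step 2: TEAE counts (events / subjects)**

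| History | Rules as written | Linked, with worsening |
|---|---|---|
| A. Pre-dose moderate, eases to mild on Day 3 | 1 / 1 | 0 / 0 |
| B. Pre-dose mild, rises to moderate on Day 3 | 1 / 1 | 1 / 1 |
| C. Post-dose onset: mild, moderate, mild | 3 / 1 | 1 / 1 |
| D. Pre-dose moderate; then mild, moderate, mild after dosing | 3 / 1 | 0 / 0 |

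**Step 3: weight of one subject.** For a subject with no other TEAE in the row concerned, the shift is 100/n points:
- ivermectin cohort: 100/6 = 16.7
- placebo cohort: 100/2 = 50
- pooled ivermectin: 100/18 = 5.6
- pooled placebo: 100/6 = 16.7

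**Step 4: what each result depends on.** History C needs neither assumption. Its records all start after dosing, whether they are dated from the change or from the original onset. Histories A and D need both assumptions, and the passages on the first of them pull in different directions:
- *For reading the baseline AE assessment as the last pre-dose check:* Protocol 7 places baseline safety assessments at the pre-dose timepoint nearest dosing, and SAP 4.1 takes the last observation before first dose as baseline. On this reading the signs in A and D are not AEs, and both cases disappear.
- *Against:* AEs count from consent, and Protocol 7.6.1.1 describes an AE as something "which either emerges, or worsens from Screening, during the clinical study", which puts the reference point at Screening.

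**The case against.** The strongest reply is that the improving case may not arise at all. If the baseline AE assessment is the last check before dosing, a sign already present then and easing later is never an AE. Nor does the protocol say what start date a continuation record takes. Both points stand, so this part can only be put conditionally. A reader might infer that the plan as written inflates the percentage of subjects with TEAEs. The documents do not support that as a statement of fact.

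The case is also likely to be uncommon. Protocol 7.6.2 has three intensity grades, so easing short of resolution requires a moderate or severe AE at first dose, in volunteers who must be healthy at Screening and Day -1. A change in frequency is another route. No rate of AEs ongoing at dosing is given, and 1/6 is simply the weight of one subject.

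Other stronger inferences also fail. Fluctuation alone does not alter subject-level incidence by SOC and PT: history C is one subject, at moderate. SAP 5.2 sets date conventions for calculating duration, but SAP 4.6.1 lists no duration summary, so shortened durations are not a planned output. The escalation criteria in Protocol 3.2.2.1 that set a number count cases or subjects, not records. The rules apply to both arms, and listings for about 24 subjects keep split records visible.

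It can also be said that counting records is a legitimate convention, since the protocol calls each change a separate event. That is arguable, but an event count that mixes new episodes with changes in old ones is hard to interpret, and the SAP does not say this is intended. The table shells and Data Management Plan might hold a linking rule. They are separate documents, and Protocol 11.3 assigns derivation algorithms to the SAP.

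**Conclusion.** The point holds in two parts of different strength.

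- **Firm.** Followed as written, the two documents count one continuous post-dose episode with k changes as k+1 events. The effect is confined to event-level counts.
- **Conditional.** If an AE with onset between consent and first dose is recorded as an AE, and its continuation record is dated from the change, an AE that improves after dosing is counted as treatment-emergent. This can also raise subject-level incidence, by 16.7 points per subject in an ivermectin cohort and 50 in a placebo cohort, provided the subject has no other TEAE in that row.

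The frequency of either cannot be estimated from the documents. The consequence is a less accurate descriptive safety profile. No formal test is planned, and the numerical escalation criteria are not directly touched. The change is worth making because the correction is small and the rule miscounts when applied literally.

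**What to change.** Add a paragraph to SAP 4.6.1 with these elements:

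1. Define a TEAE as an AE with onset at or after first dose, or a pre-dose AE whose intensity or frequency increases after first dose. Name the reference level; the counts above use the highest pre-dose grade. Protocol 7.6.2 gives no scale for frequency, so the direction of such a change has to be judged at data review.
2. Link contiguous records of the same AE (same subject and PT), with the links confirmed at blinded data review. Episodes separated by a gap stay separate.
3. Count each linked episode as one event, with first start, last stop and maximum post-dose intensity. Derive the treatment-emergent flag for the episode, not from the start date of each record.
4. Keep every individual record in the listings.

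It would also help to state what the baseline AE assessment is and what start date a continuation record takes. The cost is one derivation step and a blinded check of the links. No visits or procedures are added.
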